## **9.4 Safety and Tolerability Assessments**

### **9.4.1 Adverse events**

Where changes in severity are recorded in the Case Report Form (CRF), each separate severity of the adverse event (AE) will be reported in the listings, only the most severe will be used in the summary tables. A pre-existing condition is defined as an AE that starts before the subject has provided written informed consent and is ongoing at consent. A non-treatment emergent AE is defined as an AE which starts after informed consent but prior to dosing. A treatment-emergent AE is defined as an AE which occurs postdose or which is present prior to dosing and becomes more severe postdose.

All AEs will be listed. Treatment-emergent AEs will be summarized by population, treatment, severity and relationship to the study drug. The frequency (the number of AEs, the number of subjects experiencing an AE and the percentage of subjects experiencing an AE) of treatment-emergent AEs will be summarized by population, treatment, Medical Dictionary for Regulatory Activities (MedDRA) version 18.0 system organ class and preferred term. The summary and frequency AE tables will be presented for all causalities and those considered related to the study drug. Any serious AEs will be tabulated.

### **9.4.2 Concomitant medication**

Concomitant medication will be coded using the World Health Organization (WHO) drug dictionary (Version March 2015). Concomitant medication will be listed.

### **9.4.3 Clinical laboratory parameters**

All clinical chemistry and hematology data will be summarized by parameter and treatment together with changes from baseline, where baseline is defined as Day -1. Individual values for clinical chemistry, hematology and urinalysis data will be listed. Additionally clinical chemistry, hematology and urinalysis data outside the reference ranges will be listed.

Values for any clinical chemistry, hematology and urinalysis values outside the reference ranges will be flagged on the individual subject data listings.

#### **9.4.4 Immunogenicity**

Immunogenicity data will be listed and the frequency of positive results will be summarized. Overlaying individual profiles of titer values will also be presented over time.

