11.2.7.3. Evaluation of Immunogenicity

The frequency of antibody formation to LY3074828 and ADA titer will be determined. If a neutralization assay is performed, the frequency of neutralizing antibodies will be determined. The relationship between the presence (or absence) of antibodies and clinical parameters (AEs, etc.) will be assessed. Likewise, the relationship between the presence of antibodies and PK parameters will be assessed.

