## **9. STATISTICAL METHODOLOGY**

### **9.1 General**

Data listings will be provided for all data that is databased. Summary statistics and statistical analysis will only be presented for data where detailed in this SAP. For continuous data, summary statistics will include the arithmetic mean, arithmetic standard deviation (SD), median, min, max and N; for log-normal data (e.g. the PK parameters: area under the concentration versus time curve [AUCs] and maximum observed drug concentration [ $C_{max}$ ]) the geometric mean and geometric coefficient of variation (CV%) will also be presented. For categorical data, frequency count and percentages will be presented. Data listings will be provided for all subjects up to the point of withdrawal, with any subjects excluded from the relevant population highlighted. Summary statistics and statistical analyses will generally only be performed for subjects included in the relevant analysis population. For the calculation of summary statistics and statistical analysis, unrounded data will be used.

Mean change from baseline is the mean of all individual subjects' change from baseline values. Each individual change from baseline will be calculated by subtracting the individual subject's baseline value from the value at the timepoint. The individual subject's change from baseline values will be used to calculate the mean change from baseline using a SAS procedure such as Proc Univariate.

Data from subjects receiving placebo in the IV cohorts will be pooled to form 1 placebo group. Data will be also summarized by population (overall, Japanese and Caucasian) where appropriate. The clinical chemistry and hematology, vital signs, and electrocardiogram (ECG) data will only be summarized by population if a trend is observed.

Data analysis will be performed using SAS® Version 9.4.

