### 9.3.2 Pharmacokinetic Statistical Methodology

The PK parameter estimates following IV administration will be evaluated to delineate effects of dose proportionality. Log-transformed  $C_{max}$  and AUC(0- $\infty$ ) estimates will be evaluated in a power model with log-transformed dose as the explanatory variable. The treatment differences will be back-transformed to present the ratios of geometric means and the corresponding 90% confidence interval (CI).

Example SAS code 1:

```
proc mixed data=pk;
  by parameter;
  model lpk = ldose / alpha=0.1 residual ddfm=kr;
  estimate 'xx mg' intercept 1 ldose yy / cl; /* Log value of xx */
  estimate 'zz mg - xx mg' ldose pp / alpha=0.1 cl; /* Difference in
log values of zz and xx */
  ods output solutionf=est;
  ods output estimates=estims;
run;
```

The above analysis will also be repeated for each population separately to examine the effect of the population on dose proportionality.

For the SC dose, the bioavailability relative to IV infusion at the same dose will be evaluated via a log-transformed model. The log-transformed  $C_{max}$  and AUC(0- $\infty$ ) will be the response variables, and route of administration (IV or SC) is the explanatory variable and ratio (SC/IV), and its 90% CI will be calculated based on the model to assess the absolute bioavailability.

Example SAS code 2:

```
proc mixed data=pk;
```

```
by parameter;
class route;
model log_pk = route / residual ddfm=kr;
lsmeans route / alpha=0.1 cl pdiff;
ods output lsmeans=lsmeans;
ods output diffs=diffs;
run;
```

Additional analysis will be conducted if deemed appropriate.

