#### **9.4.6 Electrocardiogram (ECG)**

The ECG data will be obtained directly from the 12-lead ECG traces. These data include the PR, RR, QT, QTcB intervals, QRS duration and heart rate, where QTcB is the QT interval corrected using Bazett's formula. In addition, QTcF (the QT interval corrected using Fridericia's formula) will be calculated as follows:

$$QTcF = \frac{QT}{\sqrt[3]{(60/HR)}}$$

The ECG data will be summarized by treatment together with changes from baseline, where baseline is defined as Day 1 predose. Figures of mean ECG data and mean changes from baseline will be presented by treatment. The frequency of subjects with a maximum increase from baseline in QTcB and QTcF interval will be summarized for each treatment according to the following categories: >30 ms and >60 ms. In addition, the frequency of subjects with QTcB and QTcF postdose values, according to the following categories: >450 ms, >480 ms and >500 ms, will be summarized by treatment.

The relationship between concentrations of LY3074828 and changes from baseline QTcF ( $\Delta QTcF$ ) will be explored to assess the effect of LY3074828 concentration on the  $\Delta QTcF$ . Where results are taken in triplicate, the mean of the measurements will be used in the analysis. A scatter plot of the change from baseline in QTcF versus the concentrations with the fitted lines will be plotted. A linear mixed-effects model will be fitted with the  $\Delta QTcF$  as the response, the time-matched concentration as a covariate and subject as a random effect. The intercept and slope from the model along with their 90% CI will be reported.

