#### **9.4.7 Other assessments**

All other safety assessments not detailed in this section will be listed but not summarized or statistically analyzed.

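### The protocol commits to relating antidrug antibodies to adverse events and to PK, but the SAP plans neither assessment and its statement of no changes does not record the omission

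*SAP*

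**What the plan says.** Protocol 11.2.7.3 (Evaluation of Immunogenicity) sets out four items. ADA frequency and titer will be determined. Neutralizing antibody frequency will be determined if that assay is run. The other two are relationships and carry no condition: "The relationship between the presence (or absence) of antibodies and clinical parameters (AEs, etc.) will be assessed", and "the relationship between the presence of antibodies and PK parameters will be assessed". Protocol 11.2.1 leaves the detail of the analyses to the SAP.

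SAP 9.4.4 (Immunogenicity) has two sentences. The first reads "Immunogenicity data will be listed and the frequency of positive results will be summarized". The second adds overlaid individual titer profiles over time.

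Three general provisions decide what this silence means:
- SAP 3 says that the SAP overrides the protocol's statistical considerations and that substantial differences will be identified.
- SAP 9.1 says "Summary statistics and statistical analysis will only be presented for data where detailed in this SAP".
- SAP 11 reports no changes from the protocol's analyses.

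**The concern.** A reader who follows the SAP as written would produce an ADA listing, a frequency and titer plots, and would have met every stated immunogenicity requirement without relating ADA to anything. The protocol's two relationship assessments would have disappeared, and SAP 11 would tell the reader that nothing had changed.

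The Protocol Synopsis lists immunogenicity among the safety criteria, and safety and tolerability are the primary objective. PK is a secondary objective, and the protocol itself asks whether antibodies relate to it. If the method is settled only at reporting, the choice of display is made with unblinded data in hand.

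A smaller point sits in the same section. The SAP does not say whether the frequency counts subjects or samples, or whether it is limited to post-baseline results. The protocol's aim is the frequency with which antibodies to LY3074828 form. A count that mixes in antibody already present at baseline does not measure that.

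**Working it through.** **Step 1. Look for each protocol commitment in the SAP.**

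| Protocol 11.2.7.3 | Where the SAP could carry it | Found? |
|---|---|---|
| ADA frequency | 9.4.4 | Yes, counting rule not stated |
| ADA titer | 9.4.4 | Yes, as individual profiles |
| Neutralizing antibody frequency | 9.4.4 | No, but conditional in the protocol |
| ADA versus AEs and other clinical parameters | 9.4.1, 9.4.4 | No |
| ADA versus PK parameters | 9.3.1, 9.3.2, 9.4.4 | No |

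- SAP 9.4.1: "Treatment-emergent AEs will be summarized by population, treatment, severity and relationship to the study drug". Frequency tables are by population, treatment, system organ class and preferred term. ADA status is not a classifier.
- SAP 9.3.2: PK is modeled on log dose, repeated for each population, and on route. There is no ADA term or subgroup.
- SAP 10: ADA appears only in connection with the timing of a possible interim analysis.
- SAP 9.4.6, by contrast, shows how the SAP writes a relationship analysis when it intends one: "The relationship between concentrations of LY3074828 and changes from baseline QTcF" is given a plot, a model and an interval.

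Of the two unconditional relationship assessments, 0 of 2 are planned.

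**Step 2. Would the outputs be empty?**

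Inputs:
- Active subjects planned in this study (Protocol 7.1): Cohort 1 has 5 + 3 = 8, and Cohorts 2 to 6 have 3 + 3 = 6 each, so N = 8 + 5 × 6 = 38.
- Study AMAA (Protocol 5.1), 38 active subjects with ADA data: 1 positive at baseline, 7 with a post-baseline positive, 3 of those treatment-emergent.

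Proportions with Clopper-Pearson 95% intervals, and expected count = 38 × p:

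| AMAA result | p | 95% CI | Expected in 38 |
|---|---|---|---|
| Any post-baseline positive | 7/38 = 18.4% | 7.7% to 34.3% | 7.0 (2.9 to 13.0) |
| Treatment-emergent | 3/38 = 7.9% | 1.7% to 21.4% | 3.0 (0.6 to 8.1) |

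P(at least one treatment-emergent case) = 1 − (1 − p)^38. This is 0.96 at p = 0.0789, 0.47 at p = 0.0166 and above 0.99 at p = 0.2138. If AMAA rates carry over, the outputs would be small but probably not empty.

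**Step 3. Does the counting rule matter?** In AMAA, (7 − 3)/7 = 57% of subjects with a post-baseline positive did not meet the treatment-emergent definition, and 1/38 = 2.6% was positive at baseline. The reported rate depends on what is counted.

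**Step 4. Which PK quantity can be compared by ADA status?** IV doses run from 60 to 2400 mg, a ratio of 2400/60 = 40. With AUC = dose/clearance and roughly linear PK (Protocol 5.1 and 9.3), AUC would differ about 40-fold across IV cohorts with no antibody effect at all. Route matters too. At the 40% SC bioavailability seen in AMAA, apparent clearance after SC dosing would be 1/0.40 = 2.5 times IV clearance. AUC pooled across doses would therefore mainly show dose and route. Clearance or dose-normalized AUC(0-∞), viewed within dose and route, avoids this.

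**The case against.** The strongest reply is that the protocol promises an assessment, not a table or a model. With a handful of ADA-positive subjects, reading each one against the AE and PK listings could meet it. SAP 9.1 provides listings of all databased data, SAP 9.3.2 adds "Additional analysis will be conducted if deemed appropriate", and SAP 3 allows supplementary analyses. SAP 3 also says that analyses generally follow the protocol, so silence might mean that the protocol stands. The detailed outputs are in the TFL shells, which were not available.

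Much of this limits the claim. No formal model is owed, and SAP 9.4.8, which excludes inferential safety analysis, is consistent with descriptive outputs. But the clauses cited permit the assessments without planning them, and the SAP nowhere says that a listing review is how the commitment will be met. SAP 3 and 9.1 together make silence an omission, not a deferral to the protocol.

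Three stronger readings are tempting and not supported:
- A reader might infer that the SAP forbids these assessments, citing SAP 9.4.7: "All other safety assessments not detailed in this section will be listed but not summarized or statistically analyzed". That sentence does not govern here. Immunogenicity is detailed, in 9.4.4, and PK is not a safety assessment. SAP 9.1 restricts summaries and analyses, not narrative review.
- A reader might infer that the assessments will not be done. The documents do not show that. The shells or Protocol Addendum 1, which covers ADA follow-up, may contain something relevant.
- A reader might treat the AMAA projection as a forecast. It is not. In AMAA, 33 of the 38 active subjects had psoriasis. ADA was sampled at three post-baseline times (about days 22, 43 and 85), against two here (Days 29 and 85). Doses stopped at 600 mg, against 2400 mg here. The intervals cover none of these differences.

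It is also fair to say that the listings and titer profiles would let a reader separate Day 1 from later positives subject by subject. The summarized frequency would still lack a stated rule.

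**Conclusion.** The point holds as a conflict between protocol and SAP. Two assessments that the protocol commits to are absent from the SAP, and SAP 11 does not record their absence. It should be corrected, but it does not threaten the trial: no sample size, planned estimate or confidence interval changes.

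Its size is modest. About 3 treatment-emergent cases among 38 active subjects, spread over six active groups of 6 to 8, is about 3/6 = 0.5 per group. Any display will be descriptive and may contain very few positives. That favors a simple display fixed in advance. The figure assumes that AMAA rates carry over. The conclusion about the text does not depend on it.

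**What to change.** In SAP 9.4.4, add:

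1. A descriptive display or listing of treatment-emergent AEs by subject ADA status.
2. A display of individual PK values with ADA-positive subjects flagged within dose and route. Use clearance (apparent clearance for SC) or dose-normalized AUC(0-∞), not AUC pooled across doses. SAP 9.3.1 makes the reporting of clearance optional, so name the quantity that will be used.

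If either is deliberately left out, declare and justify it in SAP 11.

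In the same edit, state that ADA is counted by subject, and show Day 1 (baseline) positives separately from post-baseline positives. The Study Schedule marks the Day 1 immunogenicity sample without a time, so the SAP should say that the baseline sample is the one taken before dosing, if that is the intention. Check the TFL shells and Protocol Addendum 1 and align them.

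Cost: a few sentences and a small number of descriptive outputs. No new samples are needed, since immunogenicity is already scheduled on Days 1, 29 and 85.

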#### **9.4.5 Vital signs**

Vital signs data will be summarized by treatment together with changes from baseline, where baseline is defined as Day 1, predose. Figures of mean vital signs and mean changes from baseline profiles by treatment will be presented by treatment. Furthermore, values for individual subjects will be listed.

#### **9.4.6 Electrocardiogram (ECG)**

The ECG data will be obtained directly from the 12-lead ECG traces. These data include the PR, RR, QT, QTcB intervals, QRS duration and heart rate, where QTcB is the QT interval corrected using Bazett's formula. In addition, QTcF (the QT interval corrected using Fridericia's formula) will be calculated as follows:

$$QTcF = \frac{QT}{\sqrt[3]{(60/HR)}}$$

The ECG data will be summarized by treatment together with changes from baseline, where baseline is defined as Day 1 predose. Figures of mean ECG data and mean changes from baseline will be presented by treatment. The frequency of subjects with a maximum increase from baseline in QTcB and QTcF interval will be summarized for each treatment according to the following categories: >30 ms and >60 ms. In addition, the frequency of subjects with QTcB and QTcF postdose values, according to the following categories: >450 ms, >480 ms and >500 ms, will be summarized by treatment.

The relationship between concentrations of LY3074828 and changes from baseline QTcF ( $\Delta QTcF$ ) will be explored to assess the effect of LY3074828 concentration on the  $\Delta QTcF$ . Where results are taken in triplicate, the mean of the measurements will be used in the analysis. A scatter plot of the change from baseline in QTcF versus the concentrations with the fitted lines will be plotted. A linear mixed-effects model will be fitted with the  $\Delta QTcF$  as the response, the time-matched concentration as a covariate and subject as a random effect. The intercept and slope from the model along with their 90% CI will be reported.

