8.1.1. Inclusion Criteria

Subjects are eligible for enrollment in the study only if they meet all of the following criteria:

[1] are overtly healthy males or females, as determined by medical history and physical examination

[1a] male subjects:

will be sterile (including vasectomy) or agree to use a reliable method of birth control and will not donate sperm during the study and for 3 months following administration of the study drug

[1b] female subjects:

are women of childbearing potential who test negative for pregnancy before receiving study treatment based on serum pregnancy test and agree to use a reliable method of birth control (for example: barrier methods such as condom, sponge, or diaphragm combined with spermicide in foam, gel, or cream; hormonal contraception [oral, intramuscular, implant, or transdermal], which includes Depo-Provera, Evra, and NuvaRing; intrauterine device; or complete abstinence from sexual intercourse with men) during the study and for 3 months following administration of the study drug

or

are women not of childbearing potential due to surgical sterilization (at least 6 weeks after bilateral oophorectomy and/or hysterectomy or at least 6 weeks after tubal ligation) confirmed by medical history, or postmenopausal, defined as either:

1) spontaneous amenorrhea for at least 12 months, not induced by a medical condition or medications

or

2) spontaneous amenorrhea for 6 to 12 months with a follicle-stimulating hormone level greater than 40 mIU/mL at screening

- [2] are first-generation Japanese or are Caucasian. **CCI**

- [3] are 20 years to 64 years, inclusive, at the time of initial screening
- [4] have a body mass index (BMI) of 18.0 kg/m² to 32.0 kg/m², inclusive, at screening
- [5] have a body weight of 40.0 kg or higher for Cohorts 1 to 4 and 48.0 kg or higher for Cohort 5 and Cohort 6
- [6] have clinical laboratory test results within normal reference range for the population or investigator site, or results with acceptable deviations that are judged to be not clinically significant by the investigator
- [7] have venous access sufficient to allow for blood sampling and administration of IP as per the protocol
- [8] are reliable and willing to make themselves available for the duration of the study and are willing to follow study procedures
- [9] have given written informed consent approved by Lilly and the ethical review board (ERB) governing the site

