8.1.2. Exclusion Criteria

Subjects will be excluded from study enrollment if they meet any of the following criteria:

- [10] are investigator site personnel directly affiliated with this study and their immediate families. Immediate family is defined as a spouse, parent, child, or sibling, whether biological or legally adopted.
- [11] are Lilly employees or employees of the third-party organizations (TPOs) involved with the study
- [12] are currently enrolled in a clinical trial involving an IP or off-label use of a drug or device or are concurrently enrolled in any other type of medical research judged not to be scientifically or medically compatible with this study

- [13] have participated, within the last 30 days, in a clinical trial involving an IP. If the previous IP has a long half-life, 3 months or 5 half-lives (whichever is longer) should have passed.
- [14] are persons who have previously completed or withdrawn from this study or any other study investigating LY3074828 or any other anti-IL-23 antibody and have previously received the IP
- [15] have known allergies to LY3074828, related compounds including humanized monoclonal antibodies, or any components of the formulation or history of significant atopy
- [16] have clinically significant multiple or severe drug allergies, intolerance to topical corticosteroids, or severe posttreatment hypersensitivity reactions (including but not limited to erythema multiforme major, linear immunoglobulin A (IgA) dermatosis, toxic epidermal necrolysis, or exfoliative dermatitis)
- [17] have an abnormality in the 12-lead ECG that, in the opinion of the investigator, increases the risks associated with participating in the study
- [18] have an abnormal blood pressure as determined by the investigator
- [19] have a significant history of or current cardiovascular, respiratory, hepatic, renal, gastrointestinal, endocrine, hematological, or neurological disorders capable of significantly altering the absorption, metabolism, or elimination of drugs; of constituting a risk when taking the study medication; or of interfering with the interpretation of data
- [20] have known or ongoing psychiatric disorders
- [21] regularly use known drugs of abuse and/or show positive findings on urinary drug screening
- [22] show evidence of human immunodeficiency virus (HIV) infection and/or positive human HIV antibodies at screening
- [23] show evidence of hepatitis C and/or positive hepatitis C antibody at screening

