- c Time from starting infusion in hours, with the exception of Day -1. Time-matched ECGs and vital signs on Day -1 should approximately match the times planned on Day 1. Vital signs and ECG recording should occur prior to PK sampling, except at the end of infusion, at which time PK sampling will occur first.
- d Required for intravenous cohorts only. PK samples will be collected precisely at end of infusion. Vital signs and ECGs should be taken approximately 10 minutes after the end of infusion.
- e Not done for Cohort 3.
- f ECGs should be taken after an approximate 5-minute rest in supine position. ECGs on days without dosing should be taken close to the Day 1 dosing time, where possible. ECGs will be collected in triplicate except for screening visit.
- g All female subjects of childbearing potential will have serum pregnancy test at screening. For women who are considered to be postmenopausal, FSH should be drawn to confirm postmenopausal status as defined in inclusion criterion [1b] and to be considered exempt for further pregnancy tests during the study.
- h Time from starting infusion in hours. Samples are requested to be taken at the specified time and on days without dosing should be taken close to the Day 1 dosing time where possible. Actual times of doses and samples are to be recorded accurately to the minute on the appropriate forms.

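### The postdose QTc >450/>480/>500 ms counts do not separate subjects already above the cut-off before dosing from new cases; a minor point, mainly for QTcB >450 ms

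*SAP*

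**What the plan says.** SAP 9.4.6 plans two categorical QTc summaries by treatment. The first is relative to baseline: "The frequency of subjects with a maximum increase from baseline in QTcB and QTcF interval will be summarized for each treatment", with categories >30 and >60 ms. The second is absolute: "the frequency of subjects with QTcB and QTcF postdose values, according to the following categories: >450 ms, >480 ms and >500 ms". The absolute summary has no condition on the baseline value, and the SAP text describes no baseline-by-postdose display. A baseline exists for ECG data, "where baseline is defined as Day 1 predose".

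On entry, protocol exclusion [17] removes subjects who "have an abnormality in the 12-lead ECG that, in the opinion of the investigator, increases the risks associated with participating in the study". Inclusion [1] requires that subjects "are overtly healthy males or females, as determined by medical history and physical examination". Neither gives a value in milliseconds, and no QTc limit appears elsewhere in the protocol.

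For adverse events the SAP does separate old from new. Section 9.4.1 says: "A treatment-emergent AE is defined as an AE which occurs postdose or which is present prior to dosing and becomes more severe postdose".

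**The concern.** A count of subjects with a postdose QTc above 450 ms can be read as a count of subjects whose QTc became prolonged after dosing. As specified, it mixes two kinds of subject: those who cross the cut-off after dosing, and those who were above it on Day 1 predose and are above it again later. Nothing at entry rules out the second kind.

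Safety is the primary objective and the groups are small, so one or two subjects with a high baseline, falling by chance into one dose group, could suggest or mask a pattern across doses. The >30/>60 ms table does not resolve this, because the SAP does not cross it with the absolute categories. The AE section already makes this distinction; the QTc categories do not.

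**Working it through.** **Planned numbers.** Cohort 1 has 10 subjects and Cohorts 2-6 have 8 each: 10 + 5 x 8 = 50, which reproduces the planned total. Active: 8 + 5 x 6 = 38. Placebo: 2 + 5 x 2 = 12, of whom 10 are IV and 2 SC.

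**Weight of one subject.** In a 6-subject active group, 1/6 = 17 percentage points. At 600 mg (Cohort 1, 8 active), 1/8 = 12.5 points.

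**Assumptions.** The documents give no QTc mean or SD, so these are assumed, with no drug effect:
- QTcB: mean 415-420 ms, between-subject SD 20, within-subject SD 10.
- QTcF: mean 400-405 ms, between-subject SD 15-18, within-subject SD 7-8.
- 13 postdose ECG times, counted from the IV schedule in protocol Attachment 1 (the SC cohort has 12).
- One value per time point with independent normal errors, and no effect of ECG screening under exclusion [17].

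**Share above a cut-off c at baseline.** P = 1 - Phi((c - mean) / sqrt(SD_between^2 + SD_within^2)). For QTcB the total SD is sqrt(400 + 100) = 22.36 ms. For QTcF it is sqrt(225 + 49) = 16.55 to sqrt(324 + 64) = 19.70 ms.

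| Measure, cut-off | z | P(baseline above) | Expected among 38 active | P(at least one of 6) = 1 - (1 - P)^6 |
|---|---|---|---|---|
| QTcB >450 | 1.565 to 1.342 | 5.9% to 9.0% | 2.2 to 3.4 | 30% to 43% |
| QTcB >480 | 2.907 to 2.683 | 0.18% to 0.37% | 0.07 to 0.14 | 1% to 2% |
| QTcB >500 | 3.801 to 3.578 | 0.007% to 0.017% | 0.003 to 0.007 | 0.1% or less |
| QTcF >450 | 3.021 to 2.285 | 0.13% to 1.1% | 0.05 to 0.42 | 0.8% to 6.5% |

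**Share of the postdose count that is pre-existing.** This was simulated: baseline = subject mean + error; postdose maximum = the largest of 13 values with independent error.
- QTcB >450: 19-26% of subjects are counted (7.2 to 9.9 of 38). Of these, 29-33% were above 450 ms at baseline (2.1 to 3.2 of 38). A subject above 450 ms at baseline is counted again in 93-94% of cases.
- QTcF >450: 0.7-4.4% are counted (0.3 to 1.7 of 38), of whom 14-22% were above at baseline.

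**Wider range.** With mean 400-420, between-subject SD 15-20 and within-subject SD 8-12 ms, the pre-existing share runs from 8% to 37%, and a subject with a high baseline is counted again in 64-95% of cases. Among all 50 subjects, about 0.5 to 16 are counted, of whom about 0.06 to 4.6 are pre-existing.

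**Does the >30 ms category separate old from new?** Under the QTcB assumptions, 97-98% of pre-existing >450 ms subjects have a maximum increase of 30 ms or less, but so do 77% of new ones. Absence from the >30 ms row therefore does not identify a pre-existing case.

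**The case against.** The strongest reply is that baseline is already well covered. Section 9.4.6 plans changes from baseline, mean-change figures, the >30/>60 ms categories and a concentration model on change in QTcF. Section 9.1 lists all databased data and gives the minimum and maximum for continuous data, so with about 50 subjects the predose value of anyone counted can be looked up. Placebo columns are planned and safety inference is not. No dose-escalation or stopping criterion in the protocol uses these categories. The table shells are a separate document that was not available and may already show baseline. All of this stands, and it makes the point minor. It does not put the distinction into the summary as the SAP describes it.

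A reader might infer more than the documents support:
- That predose values are tabulated as postdose findings. They are not: a subject is counted only if a measured postdose value exceeds the cut-off.
- That the SAP presents the count as drug-related prolongation. It attaches no such label.
- That all three cut-offs and both corrections are affected alike. The figures show an effect mainly for QTcB >450 ms.
- That a baseline condition would remove the no-drug background. It removes only part: 67-71% of QTcB counts under the assumptions come from repeated measurement in subjects who started at or below 450 ms.
- That restricting the count to subjects at or below the cut-off is the same as splitting it. It is not. A subject who rises from 455 to 478 ms would leave the >450 count, would not reach >480, and with a rise of 23 ms would not enter the >30 ms category.

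**Conclusion.** The point holds as a minor one. The absolute QTc categories ignore the Day 1 predose value, no numeric entry limit keeps out subjects with high values, and the planned categories do not tell pre-existing cases from new ones.

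For QTcB >450 ms, about 6-9% of subjects would start above the cut-off and about 30% of those counted without any drug effect would be pre-existing. For QTcF fewer than one such subject is expected among the 38 active subjects, and at >480 and >500 ms the effect is negligible. These sizes depend on the assumed means and SDs. Whether any such subject enrols cannot be known from the documents. The consequence is limited to how a descriptive safety table reads; it does not bear on conduct or on any decision rule in the plan.

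**What to change.** In SAP 9.4.6, keep the all-subject count for each cut-off and treatment, and split it into:
- 'new': Day 1 predose value at or below the cut-off and a postdose value above it, with the subjects at or below the cut-off at baseline as denominator;
- 'present at baseline': above the cut-off both predose and postdose.

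A shift table of baseline category by maximum postdose category, by treatment, would serve equally well. Do not drop subjects with a high baseline from the display. If only one display is changed, QTcB >450 ms is where it matters.

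In the same edit, say whether the mean of the replicates or each single reading feeds these categories. Protocol Attachment 1 states "ECGs will be collected in triplicate except for screening visit", but the SAP's sentence on averaging sits in the concentration-QTc paragraph.

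Cost: a short change to the SAP wording and one table shell. No new data, no change to conduct and no change to entry criteria.
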